10.3.2.3. Concomitant Therapy

Not applicable.

10.3.2.4. Treatment Compliance

Not applicable.

10.3.3. Efficacy Analyses

10.3.3.1. Primary Analyses

Aim 1. Test the effectiveness of the EMC² Strategy, compared to usual care, to improve patient understanding and safe use of prescribed medications

Medication knowledge is the primary outcome of interest, and will be analyzed as a score ranging from 0-100 reflecting the percent of items correct for each medication. Associations between medication knowledge and potential confounders at the patient (socio-demographic characteristics, comorbidities, # and type of medications taken, new or changed prescription, previous history with side effects, literacy, and primary language) and medication (drug type, route of administration) levels will be examined. We intend to use generalized linear mixed models (GLMM) to account for the correlated nature of the data from patients prescribed medications from the same providers, specifying the identity link for the outcome of medication knowledge using PROC GLIMMIX in SAS (v.9.4). Treatment assignment will be the independent variable of primary interest and modeled as a fixed effect, and prescriber will be modeled as a random effect. We will also include fixed effects for any potential confounding

covariates noted in the descriptive studies. For all GLMM analyses, we will report point estimates and 95% confidence intervals, and the extent to which random effects suggest correlation of outcomes within prescribers.

Additionally, we will examine rates of missing data, and determine if there are any discernible patterns using GLMMs with a logit link function to predict the presence of missing data. Should we find significant predictors, we will use multiple imputation methods and present results as secondary analyses.

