An individual patient will be involved in the study for a total of up to 3 months. They will complete a screener enrollment interview, a T1 in person or phone interview as soon as possible following the screener, and a final T2 interview on the phone at 3 months.

[figure not shown]
We anticipate that patient enrollment will actively take place until Q2, 2020.

Our proposed/anticipated study timeline is below.

Table 4 shows study measures and outcomes.

			Inter	view			
Variable	Instrument(s) or Measure(s)		T1			T2	EHR Reviev
Covariates		_					
Socio-demographics	Age, sex, race/ethnicity, education, income, insurance/work status, living situation	Summary	•				
Baseline Health Status	Self-reported overall health/chronic conditions	ung	•				
Health Literacy	Chew		•				
Social Support	Tangible social support scale, marital status	Med	•	Week	month		
Patient Activation	Consumer Health Activation Index (CHAI)		•	Ve.	0		
Effectiveness Outcomes		and		7	Е		
Medication Knowledge	Dosage, storage, indication, risks and benefits, side-effects		•		Ξ	•	
Medication Adherence	Self report fill and time to fill	ing	•	ij	ire	•	
	Proper use	sel	•	Ĕ	na	•	
	ASK-12	Ë	•	ō	ou	•	
Fidelity Outcomes		counseling,		Questionnaire-	Questionnaire		
Provider Counseling	Receipt of provider counseling (yes/no)		•	ne	ne		
Qualify of Provider Counseling	CAHPS- communication about medicines	RX	•	g			
Receipt of Materials	Receipt of Med Guide (yes/no)	Ă,	•	rta	tal		
Perceived Helpfulness	How helpful was intervention? (1 to 10 scale)	BPA,	•	Portal	Portal		
Pharmacy Counseling	Receipt of pharmacy counseling (yes/no)		•	-	а.	•*	
Qualify of Pharmacy Counseling	CAHPS- communication about medicines	Visit-	•	1		•*	
Receipt of Portal Email	Completion of portal assessment (yes/no)					•	
	How helpful was intervention? (1 to 10 scale)	Clinic				•	
Clinic Staff Follow-Up Counseling	Receipt of counseling (yes/no)	C				•	
Quality of Clinic Staff Counseling	Self-reported clinic follow-up					•	
Frequency of Clinic Follow-Up	EHR Review of clinic contact with patient			1			•

Figure.1 Illustrates the study design

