10.1. Sample Size Determination

The sample size for this pragmatic study was based on comparisons of the primary outcome of medication knowledge between the two arms (i.e., usual care vs EMC²) at the T2 interview. We expect patients in the usual care arm to score an average of 55.6% correct responses (SD=28.4) based on a previous study that tested comprehension of the FDA standard Med Guides to those to be used in this study(9). Enrolling 330 patients and estimating 90% retention at the T2 interview (N=300, 150 per arm, 6 per provider), we will have 80% power to detect a minimum difference of 9.4% between the EMC² and the usual care arm assuming a Type I error of 5% (improving from 55.6% to 65.0% or greater). An intra-class correlation coefficient (ICC) of 0.001 was used; we expect clustering of physicians to have minimal influence on outcomes. However, even if the ICC were higher (i.e. 0.01) we could still detect a difference as small as 9.6%.

With the sample size set by the primary outcome, we also report minimum detectable differences for medication adherence measures. We estimate 65% of the usual care arm to demonstrate proper use of their medications based on prior studies(1, 18). With similar assumptions described above, a sample of 300 participants would enable us to detect a minimum absolute difference of 14.4% between arms with an ICC of 0.001 and 14.7% with an ICC of 0.01. We expect participants in the usual care arm to score an average of 27.5 (SD=7.2) on the ASK-12 based on validation studies(15). Retaining 300 participants (150 per arm, 6 per provider) at the T2 follow-up interview we will have 80% power to detect a minimum difference of 2.4 between the EMC² and the usual care arm (improving from 27.5 to 25.1 or less) using an ICC of 0.001 and a difference of 2.5 (improving from 27.5 to 25.0 or less) and with an ICC of 0.10. While no cut-off indicating non-adherence is provided, the goal would be for patients to score below 22.5, the average score in patients who took medications exactly as directed in the ASK-12 validation studies(15). We could detect differences smaller than this with the proposed sample size. In addition, differences in subscale scores of 1.3 for behavior, 0.9 for health beliefs, and 1.0 for inconvenience/forgetfulness could be detected between arms assuming mean scores of 10.5 (SD=3.8), 8.1 (SD=2.7), and 8.9 (SD=3.0), respectively, in the usual care arm.

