10.3. Statistical Analyses

10.3.1. General Statistical Considerations

We will perform analyses to address each of the aims using SAS v9.4 (Cary, NC).

The proposed trial uses a cluster-randomized design where the prescribing physician is the unit of randomization. We will randomize providers (i.e. attendings and fellows) to one of two intervention arms (usual care, EMC2). To optimize the likelihood of obtaining similar populations in each, providers will be placed into strata based on their

roles (attending, fellow) and historical volume of study medications dispensed (high, medium, low) for attendings. Providers from each strata will be randomized and identities will be revealed after randomization is complete. Patients enrolling in the study are assigned to the study arm of the provider signing their prescription within the EHR.

Given the brief follow-up period, we anticipate ~90% retention at T2 interview. These estimates result in 330 patients recruited with an anticipated 300 patients (150 per arm) available for primary data analysis.

Effectiveness analyses will be conducted on the full analysis set. This set includes all data from all randomized patients completing the outcomes of interest according to the treatment the patients were assigned.

All tests of treatment effects will be conducted at a 2-sided alpha level of 0.05, unless otherwise stated.

Any change to the data analysis methods described in the protocol will require an amendment ONLY if it changes a principal feature of the protocol. Any other change to the data analysis methods described in the protocol, and the justification for making the change, will be described in the clinical study report (CSR). Additional exploratory analyses of the data will be conducted as deemed appropriate.

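### The primary knowledge analysis uses T2 completers only and no T1 knowledge score; multiple imputation depends on a significance test and stays secondary

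*Combined protocol and SAP*

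**What the plan says.** - **Endpoint and timing.** Section 4 sets the primary endpoint as medication-specific knowledge at 3 months. Section 10.1 bases the sample size on the arm comparison at the T2 interview.
- **Analysis set.** Section 10.3.1 defines the full analysis set as follows: "This set includes all data from all randomized patients completing the outcomes of interest according to the treatment the patients were assigned". It expects 300 of 330 recruited patients in the primary analysis.
- **Evaluable population.** Table 5 (10.2) removes only patients with no post-randomization measure of the parameter being analysed.
- **T1 data.** The medication knowledge row of Table 4 (5.1), described as "Dosage, storage, indication, risks and benefits, side-effects", is marked at both T1 and T2. Section 5.2 expects the 330 recruited patients to complete the baseline assessment.
- **Primary model.** Section 10.3.3.1 specifies arm as a fixed effect, prescriber as a random effect, and confounders. T1 knowledge is not among the listed confounders, nor among the patient characteristics in 10.3.2.2. There is no visit term and no patient-level repeated measure.
- **Missing data.** Section 10.3.3.1 models the presence of missing data with logit GLMMs, then says: "Should we find significant predictors, we will use multiple imputation methods and present results as secondary analyses". No unconditional missing-data analysis is given.

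**The concern.** Some 30 to 33 patients are expected to have a T1 knowledge score but no T2 score. For them the trial already holds the most relevant predictor of the missing value, and the stated primary analysis does not use it. If loss to T2 depends on knowledge, and the loss or the gap between completers and dropouts differs by arm, the completer contrast is biased.

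The planned safeguard depends on statistical significance, which is a poor criterion for three reasons. A non-significant result with about 30 missing patients does not show that completers are representative. A significant result does not show that the variable matters for the T2 score. And when the test is significant, the imputed result is still only secondary, so the primary estimate stays as it was.

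**Working it through.** **1. The plan's own figure.** Inputs from 10.1: SD 28.4, 150 per arm at T2, 6 per provider (so 50 providers), 80% power, two-sided 5%. On clustering: "An intra-class correlation coefficient (ICC) of 0.001 was used".

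- Design effect = 1 + (6 − 1) × 0.001 = 1.005
- SE = 28.4 × √(2 × 1.005 / 150) = 3.29
- Normal approximation: (1.960 + 0.842) × 3.29 = 9.21
- Noncentral t with 50 − 2 = 48 df: 9.40, and 9.61 at ICC 0.01

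The stated 9.4 and 9.6 are reproduced with the t distribution.

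**2. Number missing.** 330 × 0.9 = 297, and the plan also uses 300, so 30 to 33 patients lack T2.

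**3. Power of the missingness test** (30 missing, 300 observed, two-sided 5%). For a T1 gap of δ SD, z = δ / √(1/30 + 1/300) = δ / 0.1915.

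| T1 gap (SD) | Points | Power |
|---|---|---|
| 0.2 | 5.7 | 18% |
| 0.3 | 8.5 | 35% |
| 0.4 | 11.4 | 55% |
| 0.5 | 14.2 | 74% |

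For a balanced binary predictor with 10% missing overall (Wald test):

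- Odds ratio 1.5 (8.2% vs 11.8% missing): ln 1.5 / 0.373 = 1.09, power 19%
- Odds ratio 2 (7.0% vs 13.0%): ln 2 / 0.383 = 1.81, power 44%

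For arm as the predictor, 165 per arm: 8% vs 12% loss gives 23% power, and 5% vs 15% gives 86%.

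**4. Chance triggering.** Section 10.3.3.1 does not name the candidate predictors. With ten independent ones (assumed) and data missing completely at random, the chance of at least one significant result is 1 − 0.95^10 = 40%.

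**5. Bias of the completer contrast.** Bias in one arm's mean = proportion lost × (completer mean − dropout mean). With an assumed 10-point gap in both arms:

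- Loss 10% vs 10%: 0.10 × 10 − 0.10 × 10 = 0
- Loss 5% vs 15%: 0.15 × 10 − 0.05 × 10 = 1.0 point

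The bias also arises with equal loss if the gap differs. A 10-point gap in one arm only, at 10% loss, gives 1.0 point.

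Simulation: 165 per arm, SD 28.4, true difference 9.4, clustering ignored. The T1–T2 correlation (0.6) and the log-odds of loss (−1 per SD of T1) are assumptions. Ranges cover repeated runs.

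| Loss, usual care vs EMC² | Completers | Using T1 within arm |
|---|---|---|
| 10% vs 10% | 9.4 | 9.4 |
| 8% vs 12% | 9.9–10.1 | 9.3–9.5 |
| 5% vs 15% | 10.7–10.9 | 9.3–9.5 |
| 15% vs 5% | 7.8–7.9 | 9.3–9.5 |

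The largest bias is about 10.9 − 9.4 = 1.5 points, in either direction, against a standard error of about 3.2 to 3.3.

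**6. Would the test fire where the bias is material?** At −1 per SD, a logit test that includes T1 knowledge is significant in over 99% of runs. At −0.2 and −0.35 per SD it is significant in about 20% and 45–50% of runs. The bias with unequal loss is then only about 0.1 to 0.7 points.

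**7. Precision.** With T1–T2 correlation ρ and 10% loss, effective n per arm = 150 / (1 − 0.10 ρ²). For ρ = 0.3, 0.5 and 0.7 (assumed) this is 151.4, 153.8 and 157.7. The minimum detectable difference falls from 9.40 to 9.36, 9.28 and 9.17, a gain of at most (9.40 − 9.17) / 9.40 ≈ 2.5%.

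**The case against.** **The condition might be thought to hide serious bias by usually failing to fire.** The calculations do not support that. Where dependence on T1 is strong enough to matter, a test that includes T1 knowledge fires almost always; where the test is weak, the bias is a small fraction of a standard error. What stands is that 10.3.3.1 neither includes nor excludes T1 knowledge as a candidate predictor, so whether the test would look in the right place is left open.

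**The condition might be thought to cause the T1 scores to be discarded.** It does not. They go unused because of the completer set and a model without T1, for every patient and not only for dropouts. Even this is an inference from the stated terms: no sentence says that T1 knowledge is discarded.

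**Differential loss is not shown.** The plan gives one overall retention figure. The T2 interview and its payment are not distinguished by arm. The extra portal emails in the EMC² arm are automated care messages, not retention contacts. All of this stands: unequal loss is possible in an open-label trial, but the documents do not predict it.

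**A T2-only comparison matches the endpoint and the power calculation.** That also stands. The estimate should remain the T2 contrast, and a joint model need not be the only acceptable primary analysis.

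**Table 5 could keep a patient with only a T1 score.** Prescribers are randomized before the study starts (7.3), so T1 is post-randomization. Read literally, such a patient has a knowledge measure and is evaluable, whereas 10.3.1 requires completion of the outcome. This does not rescue the plan, because the two definitions conflict.

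**Conclusion.** The point holds, with modest consequences. The primary analysis is a completer analysis that leaves out an already collected T1 knowledge score, and imputation rests on a poor criterion that cannot alter the primary result.

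The bias is zero when loss and its mechanism are the same in both arms. It reaches about 1.5 points, 16% of the 9.4-point target and a little under half a standard error, with 5% versus 15% loss, T1–T2 correlation 0.6 and log-odds of loss −1 per SD. Those three inputs are assumptions. Larger assumed gaps would give more: a 20-point gap with the same unequal loss gives 0.15 × 20 − 0.05 × 20 = 2.0 points. Precision improves by at most about 2.5%.

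This is a cheap improvement worth making. It is not evidence that the trial's main comparison is unsound.

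**What to change.** 1. In 10.3.3.1, delete the condition that makes imputation depend on significant predictors. The missingness models can stay as description.
2. Prespecify, whatever those models show, a missing-at-random analysis of the T2 arm contrast that uses T1 knowledge. Either of these will do: multiple imputation within arm, with T1 knowledge and prescriber in the imputation model; or a joint mixed model of the T1 and T2 scores with arm, visit, arm-by-visit, and random effects for prescriber and patient.
3. State whether this is the primary estimate or a sensitivity analysis that is always reported beside it.
4. Treat T1 knowledge as an outcome or an imputation predictor, not as a baseline covariate. It follows the index visit, so it may already carry a treatment effect, and adjusting for it could remove part of the effect being estimated.
5. Reconcile the Evaluable definition in Table 5 with the full analysis set in 10.3.1, so that the status of a patient with only a T1 score is clear.

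The cost is SAP wording and slightly more programming, with no new data collection. The downside is reliance on a missing-at-random model given T1 knowledge and arm; that assumption is weaker than what the completer analysis needs, but it cannot be verified from the data.

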10.3.3.2. Secondary Analyses

Aim 2. Test the effectiveness of the EMC² Strategy, compared to usual care, to improve patient adherence to prescribed medications

We will repeat all GLMM analyses described in Aim 1, but with medication adherence outcomes relevant to Aim 2. We will specify the logit link for binary outcomes (whether treatment was initiated (yes or no) and proper use (correct or incorrect)) and the identity link for continuous outcomes (time to fill and ASK-12 scores). We will collect data from the EHR related to the study medications (order dates, sig, quantity, type of fill, prescribing provider, etc...) needed to conduct the analyses.

10.3.3.3. Tertiary/Exploratory Analyses

Aim 3. Evaluate the fidelity of the EMC² Strategy to promote provider counseling, deliver patient Rx information, and inform providers of potential harms.

Compared to usual care, patients receiving the EMC² strategy will:

- 1) report higher rates and quality of provider Rx counseling
- 2) report higher rates of receipt of print Rx information

Appropriate bivariate analyses will be performed based on each outcome measure described below using t-tests, Wilcoxon Rank-Sum, or $\chi 2$ tests, as appropriate.

Provider Rx Counseling. We will ask patients (yes/no) whether their provider(s) (physician/nurse) counseled them on their prescribed medication. We will also ask adapted questions from the Health Literacy supplemental items of the Consumer Assessment of Health Providers Survey (CAHPS) to evaluate the extent and quality of physician verbal counseling.

Receipt of print Rx information. All patients will be asked whether they received any print Rx information at their appointment. We will further probe intervention patients to determine whether the health literate Med Guide Summary was specifically received and its perceived helpfulness. Additionally, we will also collect EHR data to determine whether the Med Guide Summary was printed with their after-visit summaries.

We will also examine completion rates of:

- 1) the EHR portal survey by patients in the intervention arm
- 2) clinic follow-up for patients identifying Rx concerns in the portal survey.

Completion of the EHR Portal Survey. Intervention patients will be asked (yes/no) whether they received the emails to visit the portal and if they completed the portal questionnaire. We will also confirm this by determining if portal questionnaire results were populated in the EHR.

Clinic follow-up for patients identifying Rx concerns. At each performance site, clinical liaisons will share with the study team what specific medication-related concerns that are self-reported by patients via the portal assessment might warrant follow-up. It is at the discretion of each clinical practice to choose how they will triage the information provided via the feedback from the EMC2 intervention, and as part of the study we will explore the frequency and nature of follow-up that occurred for various medication-related concerns by self-report and in the EHR.

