Primary • Test the effectiveness of the EMC ² Strategy, compared to usual care on improvement in patient knowledge of prescribed medications	Medication-specific knowledge measured by demonstrated proper understanding of indication, risks and benefits, and side effects at 3 months.				
Secondary • Test the effectiveness of the EMC ² Strategy, compared to usual care on improvement in safe use and adherence to prescribed medications	Medication adherence measured by fill, time to fill, demonstrated proper use, and the ASK-12. at 3 months				
Tertiary/Exploratory • Evaluate the fidelity of the EMC ² Strategy	 Patient report of provider counseling Patient report of receipt of print Rx information Completion of EHR portal survey Clinic follow-up (yes or no) for patients identifying Rx concerns via portal survey 				

Abbreviations: EMC²- Electronic health Record-based Medication Complete Communication

5. Pragmatic Study Design

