7.1. Treatments Administered

This pragmatic study involves a comparison of intervention administered with standard of care in routine care.

Study Arms.

Usual Care: For this study, current usual care includes 1) variable provider counseling without any EHR notifications or counseling support; 2) variable distribution of print medication information materials, including FDA Medication Guides in clinics and variable distribution in pharmacies; and 3) limited or variable active surveillance of medication use post-visits.

Intervention: EMC² Strategy: There are several components that will be embedded into the workflow via EHR/patient portal platforms, mostly automating their implementation. Following patient movement through a provider visit, the following 6 activities will occur:

- 1. *Physician Medication Alert:* If a prescribing physician attempts to place a new order or change to an existing study medication prescription, an EHR-generated alert will notify the provider that the medication requires patient counseling. Physicians can opt to ignore this alert.
- 2. *Provider Counseling Support:* Content from the 1-page, Med Guide Summary will appear on the screen, if selected by the provider, to orient and inform provider-patient discussion.
- 3. Automated Delivery of Med Guide + Summary: When patients leave an encounter, the medication order in Epic will automatically cue printing of both the 1-page, health literate Med Guide Summary for study medications and a full Med Guide, if applicable (latter is required by FDA for certain medications only, the former designed to enhance comprehension). If the medication was ordered during a telemedicine encounter, the Med Guide Summary will automatically populate in the patient portal.
- 4. Follow-Up Portal Questionnaire: Within 1 week post-visit, patients will receive an automated email prompting them to log on to the patient portal. Patients' will be asked to fill out a short set of questions related to medication adherence, and other medication-related concerns (i.e. cost, side effects). If patients have not completed the questionnaire within 2 days, another email reminder will be sent. The information submitted back by the patient will be stored in the EHR.

Content in question form and corresponding responses for the portal questionnaire will be revised from prior evaluation scripts and written by Drs. [name], [name], [name], and [name].

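### The Aim 3 measures of Rx information delivery count print only, although Section 7.1 delivers the Med Guide Summary by patient portal after telemedicine orders

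*Combined protocol and SAP*

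**What the plan says.** Section 7.1 gives two delivery routes for the Summary. When the patient leaves an encounter, "the medication order in Epic will automatically cue printing of both the 1-page, health literate Med Guide Summary". For remote visits the route differs: "If the medication was ordered during a telemedicine encounter, the Med Guide Summary will automatically populate in the patient portal".

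The fidelity plan follows the first route only:

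- The tertiary endpoint in Section 4 (Table 2), repeated in the Synopsis, is "Patient report of receipt of print Rx information".
- The Aim 3 hypothesis in Section 10.3.3.3 is that EMC² patients will "report higher rates of receipt of print Rx information" than usual-care patients.
- The question put to both arms is described this way: "All patients will be asked whether they received any print Rx information at their appointment".
- The record check is also about paper: "we will also collect EHR data to determine whether the Med Guide Summary was printed with their after-visit summaries".

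Two items are not tied to a route. Section 10.3.3.3 adds, for one arm only, "We will further probe intervention patients to determine whether the health literate Med Guide Summary was specifically received and its perceived helpfulness". Table 4 in Section 5.1 lists a yes/no item on receipt of the Med Guide without saying how it was received.

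**The concern.** Part of Aim 3 is to establish whether EMC² delivers Rx information to patients. Where a telemedicine order is handled as Section 7.1 intends, the patient has the Summary, but the measures that define the endpoint look for paper. Measured fidelity would then fall as the telemedicine share rises, for a reason unrelated to whether delivery worked, and the arm difference in receipt could shrink for the same reason. The trial is also meant to inform scalability (Section 5.1), and the plan provides no delivery rate for the portal route. Telemedicine may not be rare here: the protocol was adapted to COVID-19 in its interviews (Section 5.1), its ACCESS eligibility (Section 6.1) and its consent process (Appendix 3.1.1).

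**Working it through.** The documents state no fidelity figure, so there is none to reproduce. The check compares delivery routes with measures, followed by an illustration of size.

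**Routes against measures (EMC² arm)**

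| Measure | In-person order (printed) | Telemedicine order (portal) |
|---|---|---|
| Patient report of print at the appointment, both arms | yes | probably no |
| EHR: Summary printed with the after-visit summary | yes | probably no |
| Probe: Summary specifically received, EMC² arm only | yes | depends on wording and coding |

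The documents nowhere say that portal delivery counts as receipt, that portal population of the Summary will be extracted from the EHR, or that results will be split by encounter type.

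**Effect on the measured delivery rate**

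Inputs: d = true delivery by the planned route (assumed) and f = telemedicine share (not in the documents; range 0 to 50%). Assume also that no Summary is printed after telemedicine and that those patients answer no. Then

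measured print delivery = d × (1 - f).

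| f | d = 100% | d = 90% | d = 80% |
|---|---|---|---|
| 0 | 100% | 90% | 80% |
| 10% | 90% | 81% | 72% |
| 20% | 80% | 72% | 64% |
| 30% | 70% | 63% | 56% |
| 50% | 50% | 45% | 40% |

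The pilot's 80% success threshold (Section 3.2) can serve as a yardstick. The measured rate drops below it once f exceeds 1 - 0.80/d: 20% for d = 100%, and 1 - 0.80/0.90 = 11% for d = 90%.

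**Effect on the arm comparison**

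If telemedicine patients in both arms report no print, the difference becomes (p1 - p0) × (1 - f), where p1 and p0 are the EMC² and usual-care receipt rates. Power is for a two-sided 0.05 test of two proportions with 150 per arm (Section 10.1), ignoring clustering, with p1 = 80% assumed.

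- p0 = 60%: the difference is 20 points at f = 0 (power 97%), 0.64 - 0.48 = 16 points at f = 20% (80%), and 0.56 - 0.42 = 14 points at f = 30% (68%).
- p0 = 40%: the difference is 40 points at f = 0 (power above 99%) and 0.40 - 0.20 = 20 points at f = 50% (97%).
- p0 = 20%: power stays above 99% up to f = 50%.

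The understatement of the delivery rate does not depend on p0. A material loss in the arm comparison needs high usual-care print receipt.

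**The case against.** The strongest reply is that the plan has more than two measures. The intervention-arm probe and the Table 4 item name no route and could record a portal-delivered Summary. This stands in part: a reader might infer that correct portal delivery is scored as a failure throughout the plan, and the documents do not support that. The probe does not repair the endpoint, however. It sits under the print heading, leaves the route open, and is asked in one arm.

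A reader might also take it as stated that nothing is printed after a telemedicine visit. Section 7.1 says only that the Summary populates the portal. It does not say that printing is suppressed, and it is silent on the full Med Guide. The interview instrument is not in the documents either, and a patient who printed the Summary at home might answer yes. For these reasons the conclusion is that the two measures would probably miss portal delivery.

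The size is hypothetical. The telemedicine share is unknown, at f = 0 there is no effect, and this trial sets no fidelity threshold of its own. The arm contrast is probably robust if usual-care print receipt is low. The Synopsis describes no distribution of print materials in clinics under usual care, although Section 7.1 calls it variable.

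Finally, a reader might expect a null knowledge result to be blamed wrongly on poor implementation. No planned analysis conditions knowledge on print receipt, so that would be a matter of interpretation and does not follow from the plan.

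**Conclusion.** The mismatch is real on the current text. Section 7.1 has a portal route, while the between-arm endpoint and the EHR check capture print only. Following the plan as written would probably understate delivery of the Summary in the EMC² arm by the factor 1 - f. That factor assumes no printing after telemedicine and truthful answers to a print question, and f is not given.

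The reach is limited to one component of a tertiary, exploratory aim. Provider counseling, portal survey completion, clinic follow-up, and the primary and secondary outcomes are unaffected. The documents do not support reading this as a failure to record portal delivery anywhere, or as a shortfall against a threshold that the trial adopted. The change is still worth making because it is cheap and corrects the delivery rate the trial would report.

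**What to change.** 1. Extend the EHR check so that a Summary counts as delivered if it was printed with the after-visit summary or populated in the patient portal.
2. Take encounter type (in person or telemedicine) from the EHR and report delivery by encounter type.
3. Define the patient-reported endpoint, in the Synopsis, Section 4 (Table 2) and Section 10.3.3.3, as written Rx information received on paper or through the portal, and ask it identically in both arms.
4. If T1 interviews have already started, which the recruitment experience reported in Section 6.1 suggests, keep the print item unchanged and add a separate portal item, so that earlier and later answers stay comparable.

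Cost: one or two more EHR fields and one more interview item, with no extra visits. Patient-reported portal receipt will be missing for those interviewed before the change. Because every participant must have a portal account, a portal item may also draw some yes answers in usual care; reporting paper and portal answers separately keeps that visible.
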